2.1. Alternative Approaches to Primary Analysis

Results of a previous PEDIG pilot study of overminus lenses (IXT3) suggested a potential interaction between baseline control and treatment with overminus lenses. Hence, the interaction between baseline control and treatment will be tested for statistical significance in the current study by adding their interaction into the primary analysis model. It is recognized that power for this test is low, and lack of significance does not rule out interaction. For the interaction test, baseline control will be divided into two groups: 2 to less than 3.5 points, and 3.5 to 5 points. If there is significant interaction, an estimate of the treatment effect and 95% confidence interval will be obtained for each of the two baseline control subgroups.

The primary analysis will be repeated in sensitivity analyses as follows:

- The analysis will be limited to participants who received their study spectacles in time to allow for at least 4 weeks of spectacle wear relative to the outcome visit. The analysis will compare the date of spectacle receipt recorded on the 2-week phone call form and the date of the 8-week visit. For subjects who have not obtained the glasses by the time of the 2-week call, protocol monitors and site staff will follow up and have the glasses receipt date on the 2-week form edited once glasses are received.
- The analysis will be limited to subjects who were tested in their study spectacles at the 8-week visit (i.e. exclude subjects tested in trial frames).
- The analysis will be limited to subjects who have all 3 control scores obtained at the 8-week outcome visit (complete case analysis).

Note: records for participants with missing outcome data will be retained in these analyses if they meet the criteria for the analysis.

3. Secondary Outcomes

To aid in interpretation of the primary outcome comparison, 8-week control scores will be used to classify participants into those having no spontaneous tropia during all 3 control tests at distance and near, and additionally, those considered as treatment responders. The differences in treatment group proportions and 95% confidence intervals for each outcome will be calculated using the Farrington-Manning score test. If there is a significant difference (p<0.05) on the primary outcome comparison, p-values for these tests will be calculated using Barnard's test. It is recognized that power for these comparisons is low; hence, these outcomes will be considered exploratory and there will be no correction to p-values for multiplicity.

These proposed comparisons will not be adjusted for baseline distance control due to the high potential for small numbers of outcomes, making adjustment problematic. As baseline control is expected to be balanced between treatment groups due to randomization, the comparisons should be unbiased. Nonetheless, an analysis adjusted for baseline control using Poisson regression with the identity link and robust variance estimation will be performed, if possible, to confirm that adjustment does not affect conclusions from the unadjusted analyses.

3.1. Proportion with Treatment Response

"Treatment response" is defined as \geq 1-point improvement in control of the distance exodeviation (average of 3 measurements) between baseline and the 8-week outcome exam.

3.2. No Spontaneous Tropia During Control Testing

No spontaneous tropia during control testing at the 8-week primary outcome exam is defined as a score of ≤ 2 (0, 1, or 2) on all three assessments of control at distance and at near.

It is acknowledged that participants who had a score of 2 on all three assessments of distance control at baseline and scores of 2 or better at near control could potentially meet this outcome criteria without any improvement in control. Given the randomization we expect to have similar numbers of such participants in each treatment group; however, if the proportion of participants with scores of 2 or better at distance and near control differs substantially between treatment groups, the proportion with no spontaneous tropia during control testing will be compared using logistic regression adjusting for baseline distance control.

4. Analyses of Additional Treatment Outcomes

Additional analyses will report the distribution of the outcome by treatment group, and an estimate of the difference between treatment groups and a 95% confidence interval (CI) if the outcome is continuous or quasi-continuous, i.e. distance control, near control, ocular alignment, near stereoacuity, distance visual acuity, and fusional convergence, will be estimated using ANCOVA, with adjustment for baseline level of the outcome where appropriate. If ANCOVA assumptions are not met, a non-parametric method such as the Wilcoxon rank sum test will be used instead, with no adjustment for baseline level of the outcome. For ordered categorical outcomes, i.e. symptoms and suppression, each level of the outcome will be assigned an integer score, starting with 0, and the bootstrap method will be used to obtain a median and 2.5th and 97.5th percentiles on the treatment group difference, instead of a mean and 95% confidence interval. P-values for treatment group comparisons will not be reported.

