The authors retrospectively evaluated 14 patients (average age of 8.3 years; range 3 to 26 years) with IXT (mean angle of deviation 26.4Δ , range $12-45\Delta$), treated with Fresnel prisms (fully correcting the average of distance and near horizontal deviation plus any vertical). Average duration of treatment was 3.7 months and outcomes were assessed out of prism (time out of prism not provided).

Results: Control of the IXT was reported to be improved (some changed from constant XT to either IXT or exophoria, some changed from IXT to exophoria), the angle of deviation decreased on average by 4.6Δ , and mean convergence amplitudes improved by 6.2Δ at distance and 9.3Δ at near.

While the prism amounts prescribed in the aforementioned studies were fully "corrective" (prism power equaled the exodeviation angle), it was stated that the prism amount was often a mean of near and distance deviations.

In contrast to fully corrective prism, Vérnonneau-Troutman subsequently suggested in her textbook on prisms that "the *minimum* power necessary to achieve control of the exodeviation at distance" should be prescribed.¹⁶ Others also recommend that the minimum "relieving" prism that provides improved sensorimotor fusion (e.g., control, suppression, stereopsis) be prescribed.^{14, 15}

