- The participant has no NEW near esotropia by cover test while wearing the "trial" relieving prism (e.g., a microesotropia previously noted on near cover test during initial testing and also noted at this time is allowed)
- The participant has no esodeviation $>6\Delta$ on PACT at near while wearing "trial" relieving prism

Participants who fail to meet any of the above criteria will not be randomized and will discontinue study participation.

Examples:

Consider the following participants, each with a 30Δ exodeviation measured by PACT at both distance and near. These participants are now all wearing 40% relieving prism (12Δ, with 6Δ base-in in each lens) in a trial frame with habitual refractive correction. After 30 minutes of wearing prism, the participants have their deviation measured by the PACT in primary position while wearing the trial frame including relieving prism. Post-prism adaptation PACT measures are given in the following examples:

Patient is eligible based upon prism adaption and CAN be randomized.

- 1. Example 1 No Prism Adaptation: Wearing prism, the participant now measures 18Δ exodeviation at distance by PACT and 18Δ exodeviation at near by PACT, and no esotropia by cover test at
 - near. The angle has decreased by the amount of prism given, so there is no prism adaptation.
- 2. Example 2 Partial Prism Adaptation: Wearing prism, the participant now measures 30Δ exodeviation at distance by PACT and 25Δ exodeviation at near by PACT, and no esotropia by cover test at near. The distance angle has not decreased while wearing prism but the near angle has decreased while wearing prism.
- 3. Example 3 Pre-Existing Micro-Esotropia at Near: Wearing prism, the participant measures 18Δ exodeviation at distance by PACT and 18Δ exodeviation at near by PACT, but is esotropic at near by cover test (reflecting pre-existing monofixation; where, in this case, the tropia and phoria are in the opposite direction). The esotropia was present prior to prism adaptation. The PACT angle has decreased by the amount of prism given, so there is no prism adaptation.

Patient is NOT eligible based upon prism adaption and CANNOT be randomized.

1. Example 1 - Full Prism Adaptation: Wearing prism, the participant now measures 30Δ exodeviation by PACT at distance and near with the prism in place. The patient has completely adapted to the prism and is NOT eligible due to complete prism adaptation.

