- 2. Example 2 New Esotropia at Near: Wearing prism, the participant now measures 18Δ exodeviation at distance by PACT and 4Δ esodeviation at near by PACT and has an esotropia by cover test at near. The participant did not previously have an underlying esotropia. This participant is NOT eligible due to the new esotropia at near.
 - 3. Example 3 Esodeviation at Near now >6Δ by PACT:
 Wearing prism, the participant measures 18Δ exodeviation at distance by PACT and 8Δ esodeviation at near by PACT, although the participant is not esotropic at near by cover test. This participant is NOT eligible due to an esodeviation >6Δ at near by PACT while wearing prism.

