4.3.3 Risk Assessment

1072 It is the investigators' opinion that the protocol's level of risk falls under DHHS 46.404, which is 1073 research not involving greater than minimal risk.

1074 1075

4.4 **Reporting Adverse Events**

1076 Although no adverse events are anticipated as a result of prism therapy or non-prism spectacle 1077 wear, any new cases of amblyopia or new cases of constant esotropia will be reported. No

surgical procedures are part of the protocol and no treatments are being prescribed that are not part of usual care. Investigators will abide by local IRB reporting requirements.

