5.2.1 Decision Guideline for Determining Whether to Proceed to a Randomized Trial

The data collected in this short-term, pilot randomized trial will primarily be used to determine whether to proceed to a full-scale, longer-term randomized trial of prism vs. non-prism. A decision guideline has been developed to aid in this decision (see below). The side effect profiles in each treatment group will also be considered when deciding whether to proceed with a full-scale trial.

1148 1149 1150

1151

1152 1153

1154

1155

1156

1157

The decision guideline for determining whether to proceed to a full-scale randomized trial will be based on the primary analysis estimate of the treatment group difference in mean distance control scores at 8 weeks. The standard deviation of 8-week distance control in IXT3 was 1.5 points (95% CI = 1.2 to 1.8 points). The convenience sample of 64 participants yields relatively low statistical power (61%) for detecting a difference if the true difference = -0.75 assuming an SD in the current study of 1.5 points and accounting for up to 5% loss to follow up. As the statistical power is poor, the decision guideline was based solely on the size of the observed difference in mean control scores (prism – non-prism). The decision is:

- **Proceed** if the observed difference < -0.75 points 1158
- 1159 • Uncertain if the observed difference favors the prism group by less than 0.75 points (diff <0 1160 and > -0.75)
- 1161 • **Do not proceed** if the observed difference is zero or favors the non-prism group (diff ≥ 0)

1162 1163 1164

*Note that differences (prism – non-prism) favoring prism will be negative given that lower control scores indicate better control.

1165 1166

1170

1171 1172

1173 1174

1175 1176

1177 1178

1179 1180 1181

1182 1183

1184

1185

1186 1187

1188

1189

1190

1191 1192

1193 1194 1195

1196 1197

1201

Decision Guideline #1: Whether to Proceed to	TRUI	(Prisn	nent Gro 1 – Non- in point	. ,	erence
Full-Scale Randomized Trial Based on OBSERVED Difference in Means in Pilot Study	-0.25	-0.50	-0.75	-1.0	-1.25
Proceed** if observed difference is ≤-≤0.75	11%	27%	50%	73%	89%
Uncertain if observed difference is <0 and > -0.75	62%	62%	46%	26%	11%
Do not proceed if observed difference is ≥0	27%	11%	4%	1%	0%

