4.3 Ocular Alignment

- The distribution of ocular alignment at distance and near fixation by PACT will be
- described for the enrollment exam and the outcome exam for each treatment group.
- Because participants in the prism group will have PACT measured at 8-weeks while

wearing study-prescribed relieving prism, the magnitude of the prescribed prism will be added to the deviation by PACT while wearing prism to obtain the total underlying deviation. The distribution of change in ocular alignment will also be described for each treatment group.

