5.2 Prism Adaptation Test (PAT) Screening Study

In addition to the randomized trial, a separate analysis will include all participants undergoing prism adaptation testing as part of screening for the randomized trial, regardless of whether they are eligible for randomization based on the results of prism adaptation testing. The participants to be included will have met all randomized trial eligibility criteria other than that relating to the outcome of the prism adaptation test. The proportion and 95% confidence interval of prism adaptation test-screened participants who fully prism adapt will be estimated. Fully adapting to prism is defined as having magnitude of PACT at distance and/or near angle while wearing "trial" relieving prism for 30 minutes (measured through the prism) which is ≥ the original PACT measurement at the same testing distance. The PACT magnitudes with and without prism are directly compared with one another and do not take into account the amount of prism being worn for testing (in contrast to the 8-week outcome PACT described in section 4.3 in which the magnitude of the prescribed prism will be added to the deviation by PACT while wearing prism for analysis of the total underlying deviation).

For PACT at distance and near, scatterplots will be used to visualize the relationship between the original without-prism test and the subsequent with-prism test.

In addition, the proportion and 95% confidence interval of screened participants who are eligible for randomization following the PAT will be calculated. Participants who meet who meet all three of the following criteria while wearing relieving prism are eligible for randomization

- Not fully prism adapted
- No NEW esotropia by cover test at near (while wearing relieving prism) note that a participant with esotropia at near while wearing prism is eligible for randomization IF an esotropia at near (of any magnitude) was present during the original testing without prism.
 - No esodeviation $>6\Delta$ on PACT at near (while wearing relieving prism)

257258259

256

Note that the analysis plan in the protocol erroneously refers to "repeat enrollment prism adaption testing;" repeat enrollments were not part of this protocol.

260261

262

263

264

265266

267

268269

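### Does leaving 'Not applicable' uncoded on the control scale let near overcorrection in prism pass as success, unseen at 8 weeks?

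*SAP*

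**What the plan says.** - **Scale.** Protocol 2.4 grades exotropia from 0 to 5, separately at distance and near. It adds an unnumbered Not applicable level for a child without an exodeviation. A child who shows no spontaneous exotropia in the 30-second observation moves to the 0, 1 or 2 part of the scale.
- **Outcomes that use it.** SAP 3.2 (as Protocol 5.4) needs scores that are "0, 1, or 2) on all three assessments of control at distance and at near". SAP 4.2 treats near control like distance control. SAP section 2 has a rule for control tests that were not performed, but nothing covers Not applicable. For the parent survey, SAP 4.5 does say what happens to not-applicable answers.
- **Test condition.** Under Protocol 3.7 all 8-week tests are done in the study spectacles, and the masked examiner performs a cover test at distance and near.
- **Alignment.** In SAP 4.3, for the prism group, "the magnitude of the prescribed prism will be added to the deviation by PACT while wearing prism".
- **Screening.** Protocol 2.7 requires of each child: "The participant has no NEW near esotropia by cover test while wearing the" trial prism. It also bars more than 6 Δ eso at near on PACT. Its example of a child 4 Δ eso with a new esotropia ends: "This participant is NOT eligible due to the new esotropia at near". SAP 5.2 repeats the criterion, "No NEW esotropia by cover test at near (while wearing relieving prism", for the enrollment test only.
- **Safety.** Protocol 4.4 states that "new cases of constant esotropia will be reported". On the decision to go on to a full-scale trial, Protocol 5.2.1 adds: "The side effect profiles in each treatment group will also be considered when deciding whether to proceed".

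**The concern.** The outcome scale looks only for exotropia, and the treatment pushes the eyes the other way. A child with a large distance angle and a small near angle receives prism sized to the larger angle and may be straight or eso at near while wearing it. If Not applicable is taken as no spontaneous exotropia, that child passes the near half of SAP 3.2 and gets the best near score in SAP 4.2. SAP 4.3 then adds the prism back and lists an ordinary exodeviation. The 8-week cover test, which could show a manifest esotropia, appears in no planned analysis, and the adverse-event wording covers only constant esotropia.

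The protocol treats new near esotropia in prism as a reason not to randomize, and side effects are to inform the proceed decision. So it seems that a harm confined mainly to one arm could be recorded as benefit in that arm.

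**Working it through.** **1. Prism dose.** Table 1 is 40% of the larger PACT. For 16, 18, 20, 25, 30 and 35 Δ this gives 6.4, 7.2, 8, 10, 12 and 14, against the listed 6, 7, 8, 10, 12 and 14. The table reproduces. The 61% power in Protocol 5.2.1 concerns distance control and does not enter here.

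**2. Can a child be eso at near in prism?** Inputs are the eligibility limits in Protocol 2.2 (distance 16 to 35 Δ, near 10 to 35 Δ, near minus distance at most 10 Δ) and Table 1. I assume measured steps of {16, 18, 20, 25, 30, 35} at distance and {10, 12, 14, 16, 18, 20, 25, 30, 35} at near. That leaves 7 + 7 + 8 + 9 + 9 + 9 = 49 eligible pairs. With f the fall in angle by 8 weeks and a the share of prism adapted to,

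in-prism near = near − f − (1 − a) × prism.

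| f (Δ) | a | Eso pairs of 49 | Largest eso (Δ) | Pairs beyond 6 Δ |
|---|---|---|---|---|
| 0 | 0 | 3 | 10 − 14 = −4 | 0 |
| 4.6 | 0 | 16 | 10 − 4.6 − 14 = −8.6 | 3 |
| 4.6 | 0.25 | 8 | 10 − 4.6 − 10.5 = −5.1 | 0 |

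The three pairs in the first row (distance/near) are 35/10, 35/12 and 30/10; three more (25/10, 30/12, 35/14) are exactly zero. With f = 4.6, 2 pairs remain eso at 50% adaptation and none at 75%.

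The 4.6 comes from the retrospective series of 14 patients in Protocol 1.3, where "the angle of deviation decreased on average by" that amount. They wore fully correcting prism, and the protocol does not say whether the figure is a near angle. It is an assumption here. The counts are grid cells and show what is reachable; they are not shares of patients.

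**3. What the add-back does.** In-prism near + prism = near − f + a × prism. Its minimum is 10 − 4.6 = 5.4, so no pair appears as eso in any row. The 35/10 child at −4 is listed as −4 + 14 = 10 exo.

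**4. Does the primary outcome move?** The smallest distance residual is for distance 16, near 25, prism 10: 16 − 10 = 6 exo, or 6 − 4.6 = 1.4 exo with the fall. That one pair crosses zero only if the 4.6 fall, no adaptation and a lens 3 Δ too strong (the tolerance in Protocol 3.7) coincide: 16 − 4.6 − 13 = −1.6.

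**5. What the coding could do to SAP 3.2 and 4.2.** With 30 children per arm, a Not applicable child who also passes all three distance tests moves the prism proportion by 1/30 = 3.3 points between success and failure. As an illustration (assumed counts), take 10/30 against 7/30, with 3 of the 10 Not applicable at near:

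| Coding | Difference | Score 95% CI |
|---|---|---|
| Success | 10/30 − 7/30 = +10.0 points | −12.9 to 32.1 |
| Failure | 7/30 − 7/30 = 0.0 | −21.6 to 21.6 |
| Missing | 7/27 − 7/30 = +2.6 points | −19.7 to 25.3 |

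All three intervals span zero widely. For near control, scoring 3 of 30 as 0 instead of leaving them out changes the mean by 27m/30 − m = −0.1m, which is −0.10 to −0.30 points if the others average m = 1 to 3.

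**The case for a change.** The strongest case for acting is that the gap is real and the remedy cheap. Success, missing and failure are all possible codings, and the SAP settles the same question for its survey but not for the control scale. The state is reachable in eligible children and belongs mainly to one arm. The plan checks for it after 30 minutes of prism and not after 8 weeks, although the masked cover test and the in-prism PACT are already collected. With 30 prism children, at least one case would be seen with probability 1 − 0.95^30 = 78.5% at a 5% rate, or 1 − 0.90^30 = 95.8% at 10%.

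Part of this stands. The coding is unwritten, and apart from adverse-event reports of new constant esotropia no planned 8-week output shows an esophoria or a non-constant esotropia in prism.

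The rest is weaker:

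- Read literally, an unnumbered level is not a score of 0, 1 or 2, so the favourable coding is an inference. It is also the sensible one: the scale measures exotropia, and a child without an exodeviation shows none. A written rule would record what an analyst would do anyway.
- Near status does not deliver success in SAP 3.2, because all three distance scores must pass too.
- Screening with the same prism accepts up to 6 Δ eso at near without a new esotropia. With no fall in angle every eso pair lies within that limit; with the 4.6 fall and no adaptation, 13 of 16 do.
- The add-back answers its own question, the underlying deviation, which is what compares with the prism-free enrollment PACT. The in-prism reading stays in the data.
- The side effects the plan does define, symptom and spectacle surveys, are tabulated by arm, as are stereoacuity and suppression.
- The 5% and 10% rates are assumed; the documents give none.

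**Conclusion.** No change to the plan is called for. The missing code is a gap that analysts fill sensibly, and what else could be asked for is one more descriptive table in a pilot. The outcomes that depend on the code are SAP 3.2, which the SAP declares exploratory, and near control, which is reported without p-values. The coding can shift their estimates (3.3 points per affected child in SAP 3.2, 0.10 to 0.30 points in the near mean for three children), but within intervals far too wide for a conclusion to turn on it.

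The primary distance outcome and the numerical proceed guideline are unaffected unless three unfavourable assumptions are stacked, and then for one grid pair by 1.6 Δ. Near overcorrection that the protocol names as reportable, new constant esotropia, is captured. A milder near esodeviation can be listed at any time from data already held, so nothing is lost by leaving the text alone.

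This rests on the assumed PACT grid, on Table 1 prism being delivered within tolerance, and on a frequency of near overcorrection that the documents do not give. The scoring manual cited in Protocol 2.4, which may settle how examiners record the level, was not available.

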4.5 Adverse Symptoms of Intermittent Exotropia and Prism Spectacle Wear

Adverse symptoms of IXT will be assessed at enrollment and 8-week outcome exam using a symptom survey that is administered to the child. Response options are based on frequency of observations: 0=never, 1=sometimes, and 2=always.

Similarly, adverse symptoms that may be associated with prism spectacle wear will be assessed at enrollment and at the 8-week outcome exam using a spectacle survey that is administered to the parent. Response options are based on frequency of observations: 0=never, 1=rarely, 2=sometimes, 3=often, 4=always, and not applicable. Percentage of not applicable responses will be calculated, but these responses will not be included in the treatment comparisons.

The distribution of scores on each survey item will be described for the enrollment exam and the outcome exam for each treatment group.

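### The bootstrap comparison of symptom items and suppression names no baseline term; adjusting for the enrollment score would sharpen it at little cost if scores persist moderately over 8 weeks

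*SAP*

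**What the plan says.** SAP section 4 sets two routes for the additional outcomes. For continuous or nearly continuous ones, the group difference "will be estimated using ANCOVA, with adjustment for baseline level of the outcome where appropriate"; if the model assumptions fail, an unadjusted non-parametric method replaces it. For suppression and symptoms, the rule is that "each level of the outcome will be assigned an integer score, starting with 0, and the bootstrap method will be used". The resampled distribution then serves "to obtain a median and 2.5th and 97.5th percentiles on the treatment group difference". No covariate is mentioned for this second route. The section closes with "P-values for treatment group comparisons will not be reported".

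The enrollment scores are part of the planned data. SAP section 4.5 states for the two surveys: "The distribution of scores on each survey item will be described for the enrollment exam and the outcome exam for each treatment group". The SAP's suppression paragraph likewise tabulates both visits. For the parent spectacle survey, SAP 4.5 adds: "Percentage of not applicable responses will be calculated, but these responses will not be included in the treatment comparisons".

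On the use of these data, Protocol 1.14 lists the proportion of participants reporting adverse effects among the outcomes informing the decision on a full-scale trial. Protocol 5.2.1 says that side-effect profiles "will also be considered when deciding whether to proceed with a" larger trial, but bases the formal guideline on the observed difference in mean distance control alone. Protocol 5.5.5 labels suppression exploratory.

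**The concern.** The ordered outcomes are treated less efficiently than the continuous ones, although the enrollment score is available for both. For alignment, stereoacuity and visual acuity the SAP also describes change from enrollment. For symptoms it describes only the two visits separately, so no stated symptom analysis links a child's 8-week answer to that child's enrollment answer. Randomization is stratified by distance control only (Protocol 2.8), so nothing in the design balances baseline symptoms.

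Headache and eye strain can be present before any prism is worn. With about 30 children per arm, a chance difference in baseline symptoms adds noise to an unadjusted comparison. At stake is how clearly the pilot can show, or fail to show, a prism side effect when the investigators weigh side effects alongside the primary result.

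**Working it through.** **The plan's own figure.** The documents state one power figure, 61%, for a true difference of -0.75 in distance control with SD 1.5 and 30 per group (Protocol 5.2.1). The standard error is 1.5 x sqrt(2/30) = 0.387, and 0.75/0.387 = 1.936. One-sided at 0.05, power is Phi(1.936 - 1.645) = 61.5%, or 60.6% with the noncentral t. The figure reproduces and confirms the planning basis of 30 per group. It concerns distance control and is unaffected by this point. No precision or power is stated for symptoms or suppression.

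**Inputs for the check**

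- 30 analyzed per group, N = 60 (Protocol 5.1).
- Correlation r between enrollment and 8-week item scores: not in the documents. Assumption, range 0 to 0.7.

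**Formula.** Relative to the unadjusted difference, the standard error of the baseline-adjusted difference is approximately sqrt((1 - r²) x (1 + 1/(N - 4))). The second factor, 1 + 1/56, is the price of estimating the slope. The equivalent sample size per group is 30 divided by the squared ratio.

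| Assumed r | Squared ratio | SE ratio | Change in SE | Equivalent n per group |
|---|---|---|---|---|
| 0 | 1.018 | 1.01 | +1% | 29.5 |
| 0.3 | 0.926 | 0.96 | -4% | 32.4 |
| 0.5 | 0.763 | 0.87 | -13% | 39.3 |
| 0.7 | 0.519 | 0.72 | -28% | 57.8 |

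Break-even: 1 - r² = 56/57, so r = sqrt(1/57) = 0.13.

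**Check on ordinal scores.** Scores with 3, 4 and 5 levels were simulated (30 per group, 4000 replicates, assumed category shares). The SE ratio was 0.97 to 0.99 at observed correlations of 0.22 to 0.25, 0.91 to 0.93 at 0.38 to 0.42, and 0.78 to 0.83 at 0.56 to 0.62. At zero correlation it was about 1.01. This agrees with the formula.

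**Chance imbalance.** The standard deviation of the baseline difference between arms is sqrt(2/30) = 0.26 SD. At r = 0.5 the unadjusted outcome difference carries 0.5 x 0.26 = 0.13 SD of it. This is the same loss of precision seen from another side, not an addition to it.

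**If children without a usable baseline score were dropped.** Adjustment would only break even if the share with a baseline score were at least 93% (r = 0.3), 76% (r = 0.5) or 52% (r = 0.7). So a rule that keeps them is needed.

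**Change scores are not a substitute.** In the same simulation, the standard error of the change-score difference was 1.20 to 1.24 times the unadjusted one at observed r of 0.22 to 0.25, and 1.06 to 1.12 times at 0.38 to 0.42. It was smaller (0.86 to 0.93 times) only at 0.56 to 0.62.

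**The case against.** The strongest reply is that this is an optional refinement of descriptive outcomes in a convenience-sample pilot that reports no p-values for them. Several parts of it stand.

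- **Unbiasedness.** A reader might infer that the planned comparison is biased or wrong. It is not: randomization protects the unadjusted difference, its interval already allows for chance imbalance, and the item tables by visit would make an imbalance visible.
- **Silence, not prohibition.** A reader might infer that the SAP rules out adjustment, or that it adjusts all continuous outcomes without exception. It does neither. It names no baseline term for the bootstrap, and for continuous outcomes it adjusts where appropriate, with an unadjusted fallback.
- **The decision.** A reader might infer that the loss of precision could tip the go/no-go rule. The documents do not support that: the rule rests solely on distance control, and side effects enter without a threshold. Suppression is not a side effect.
- **Size of gain.** It depends wholly on an assumed correlation. A low value is plausible for the parent survey: Protocol 2.4 lets a child enroll without spectacles, while Protocol 3.3 puts every randomized child in them, so the two visits may not capture the same experience.
- **Cost.** Adjustment is cheap but not free. Enrollment answers may be not applicable, and Protocol 2.5 allows enrollment without completed suppression testing.

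One part does not stand. Sparse items are said to break the resampled regression: if only 1 or 2 of 60 children have a non-zero baseline value, (59/60)^60 = 36% or (58/60)^60 = 13% of resamples contain none. In those resamples the constant column can be dropped and the treatment coefficient remains estimable. SAP section 3 does cite small numbers against adjusting its binary secondary outcomes, yet it still plans an adjusted check there where possible.

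**Conclusion.** The point holds as a minor one about precision. SAP section 4 leaves the ordinal comparison without a baseline term although the enrollment scores are collected. With 30 per arm, adjustment would lower the standard error by about 4%, 13% or 28% at correlations of 0.3, 0.5 or 0.7, would break even near 0.13, and would raise it by about 1% at zero. The correlation is an assumption throughout, so the actual gain is unknown; the possible loss is small. The relevance to the proceed decision is real but modest for the symptom items, and does not extend to suppression.

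**What to change.** State in SAP section 4 how baseline enters the bootstrap:

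1. In each resample, regress the 8-week item score on treatment and that item's enrollment score, and take the bootstrap distribution of the treatment coefficient.
2. Where the enrollment value is not applicable (parent survey) or missing (suppression), set it to a constant and add an indicator, so that no child is lost for lack of a baseline score. The SAP's exclusion of not-applicable answers at 8 weeks is unchanged.
3. Drop any baseline or indicator column that is constant within a resample.
4. Report the unadjusted difference and the planned item distributions alongside.

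The cost is a few sentences in the SAP and minor code. No new data are needed. The downside is one or two extra model terms, and intervals about 1% wider if baseline turns out to be uninformative.
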